4 SELECTION AND WITHDRAWAL OF SUBJECTS

4.1 Inclusion Criteria

Patients must meet all of the following criteria to be eligible.

1. Pathologically or cytologically confirmed GC or GEJ cancer, with evidence of being unresectable, locally advanced, or metastatic; histologically confirmed adenocarcinoma mainly.
2. Aged 18 or above, male and female.
3. Patients who have not received systemic treatment (including HER-2 inhibitors) for advanced or metastatic GC/GEJ. Subjects who have received adjuvant or neoadjuvant therapy (including chemotherapy, radiotherapy, or radiochemotherapy) for GC/GEJ must have completed the last treatment at least 6 months prior to the first dose of study treatment. Palliative radiotherapy is permitted, but it must be completed 2 weeks prior to the start of study treatment.
4. Eastern Cooperative Oncology Group (ECOG) performance status of 0-1.
5. With measurable lesion as per RECIST 1.1 criteria.

6. Life expectancy > 12 weeks.
7. All acute toxicities due to previous anti-tumor treatments or surgeries must have resolved to Grade 0–1 (as per NCI CTCAE 4.03) or to the level specified in the inclusion/exclusion criteria. Other toxicities such as alopecia, which do not pose a safety risk to the subjects evaluated by investigators, are excluded.
8. With adequate organs and bone marrow functions, as defined below:
 - a) Absolute neutrophil count (ANC) $\geq 1500/\text{mm}^3$ ($1.5 \times 10^9/\text{L}$);
 - b) Platelet count (PLT) $\geq 100,000/\text{mm}^3$ ($100 \times 10^9/\text{L}$);
 - c) Hemoglobin (Hb) $\geq 9 \text{ g/dL}$ (90 g/L);
 - d) Serum creatinine $\leq 1.5 \times$ upper limit of normal (ULN), or creatinine clearance $\geq 60 \text{ mL/min}$;
 - e) Total bilirubin (BIL) $\leq 1.5 \times$ ULN;
 - f) Aspartate transaminase (AST/SGOT) or alanine transaminase (ALT/SGPT) $\leq 2.5 \times$ ULN; for patients with liver metastasis, ALT and AST should be $\leq 5 \times$ ULN;
 - g) International normalized ratio (INR) ≤ 1.5 , prothrombin time (PT) and activated partial thromboplastin time (APTT) $\leq 1.5 \times$ ULN;
 - h) Urine protein $< 2+$; If urine protein is $\geq 2+$, then the 24-hour urine protein must be $\leq 1 \text{ g}$;
 - i) Thyroid stimulating hormone (TSH) \leq ULN; in case of abnormalities, T3 and T4 levels should be measured; if T3 and T4 levels are normal, the subject can be enrolled.

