5.2 Dose Modification of Study Drugs

5.2.1 Dose modification of SHR-1210

Dose increases and reductions of SHR-1210 are not permitted. If SHR-1210 treatment is interrupted due to a toxicity, the subject may resume the treatment at the original dose after the toxicity is resolved. AEs related to SHR-1210 may be immune toxicities, and may occur shortly after the first dose or several months after the last dose. If the conditions listed in [Table 7](#) occur, the use of SHR-1210 should be interrupted. During the study, the investigator must consult with the sponsor if the investigator considers that an adjustment listed in [Table 7](#) is inappropriate based on the benefit-to-risk ratio of subjects or that SHR-1210 treatment should be interrupted or resumed due to a condition not listed in the table.

Table 7. Dose modification criteria for SHR-1210 due to immune-related toxicity

SHR-1210-Related Toxicity	Grade for Interruption	Resumption	Discontinuation
Diarrhea/Colitis	Grade 2-3	Recovered to Grade 0-1	Toxicity has not resolved by 12 weeks after the last dose, or the corticosteroid dose cannot be reduced to prednisone 10 mg/day (or equivalent) or lower within 12 weeks after the last dose.
	Grade 4	Discontinuation	Discontinuation
AST/ALT or Bilirubin Increased	Grade 2	Recovered to Grade 0-1	Toxicity has not resolved by 12 weeks after the last dose, or the corticosteroid dose cannot be reduced to prednisone 10 mg/day (or equivalent) or lower within 12 weeks after the last dose.
	Grade 3-4	Discontinuation ^a	Discontinuation
Type 1 Diabetes Mellitus (new onset) or Hyperglycemia with Signs of β-cell Failure	Grade 3-4 or new-onset type 1 diabetes	SHR-1210 treatment may only be resumed after the clinical and metabolic conditions of the subject are stabilized.	
Hyperthyroidism	Grade 3	Toxicity reduced to Grade 0-1	Toxicity has not resolved by 12 weeks after the last dose, or the corticosteroid dose cannot be reduced to prednisone 10 mg/day (or equivalent) or lower within 12 weeks after the last dose.
	Grade 4	Discontinuation	Discontinuation
Hypothyroidism	Grade 2-4	Study treatment can be continued after starting thyroxine replacement therapy	

SHR-1210-Related Toxicity	Grade for Interruption	Resumption	Discontinuation
Pneumonia	Grade 2	Toxicity reduced to Grade 0-1	Toxicity has not resolved by 12 weeks after the last dose, or the corticosteroid dose cannot be reduced to prednisone 10 mg/day (or equivalent) or lower within 12 weeks after the last dose.

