	Grade 3-4	Discontinuation	Discontinuation
Immune-Related Hypophysitis	Grade 2-3	The SHR-1210 treatment may continue after the toxicity reduces to Grade 0-1 and the hormone replacement therapy starts.	Toxicity has not resolved by 12 weeks after the last dose, or the corticosteroid dose cannot be reduced to prednisone 10 mg/day (or equivalent) or lower within 12 weeks after the last dose.
	Grade 4	Discontinuation	Discontinuation
Renal Failure or Nephritis	Grade 2	Toxicity reduced to Grade 0-1	Toxicity has not resolved by 12 weeks after the last dose, or the corticosteroid dose cannot be reduced to prednisone 10 mg/day (or equivalent) or lower within 12 weeks after the last dose.
	Grade 3-4	Discontinuation	Discontinuation
Infusion reactions	Grade 2 ^b	Symptoms disappeared	Discontinue the drugs if the symptoms recur after adequate premedication.
	Grade 3-4	Discontinuation	Discontinuation
Other T-related toxicities ^c	Grade 3	Toxicity reduced to Grade 0-1	Toxicity has not resolved by 12 weeks after the last dose, or the corticosteroid dose cannot be reduced to prednisone 10 mg/day (or equivalent) or lower within 12 weeks after the last dose.
	Grade 4	Discontinuation	Discontinuation

Treatment should be discontinued if any grade ≥ 3 treatment-related AE recurs (grade ≥ 2 pneumonia) or any life-threatening event recurs.

- a) For subjects with liver metastasis and grade 2 AST or ALT increased at baseline, if the AST or ALT increased $\geq 50\%$ from baseline persists for at least 1 week, the treatment shall be discontinued.
- b) If the symptoms resolve within 1 hour after dechallenge, and the infusion can be resumed at 50% of the initial infusion rate. Otherwise, the treatment can only be resumed until symptoms are fully resolved. Premedication is required prior to the next dose. Refer to section 5.6.2 "Recommendations on infusion reaction management" for further management.

- c) For subjects with intolerable or persistent grade 2 treatment-related AEs, the investigator may consider interrupting SHR-1210 treatment if appropriate, and the treatment should be discontinued if toxicity fails to decrease to Grade 0-1 within 12 weeks after the last dose.

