5.2.3 Dose modification of apatinib mesylate

Dose modifications caused by apatinib-related toxicities include the following: treatment interruption (no more than 28 days), dose reduction (to 375 mg qd or 250 mg qd, depending on the initial dose of apatinib), and permanent discontinuation.

The treatment may be delayed and the dose be reduced for Grade ≥ 3 hematologic toxicity or ≥ 2 non-hematologic toxicity; for non-hematologic toxicity, manageable nausea and vomiting, and fever (below 38 $^{\circ}\text{C}$) of determined cause, active symptomatic treatment can be administered first. There is no need to immediately delay the treatment or reduce the dose.

In case of apatinib-related toxicity, administration should be delayed until recovery, and then the original dose should be resumed or the dose should be reduced by one dose level. The minimum dose allowable is 250 mg/d. If the dose is still intolerable at the reduced dose of 250 mg/d, apatinib should be permanently discontinued (refer to [Table 9](#) for the recommended dose modification method). Dose increase of apatinib is not allowed during the study period.

Table 9. Recommended dose modification of apatinib

Apatinib-Related Toxicities	Grade	Dose Delay or Not	Criteria for Resuming	Dose Modification Method	Criteria for Discontinuation
Hematologic Toxicity	Grade 1-2	No	—	—	—
	Grade 3	Yes	Until the toxicity recovers to Grade ≤ 2	Resume at original dose	Apatinib interruption for more than 28 days
	Grade 4		Until the toxicity recovers to Grade ≤ 2	Reduce the dose by one level	
Non-Hematologic Toxicity	Grade 1	No	—	—	—
	Grade 2 (last for ≥ 7 days)	Yes	Until the toxicity recovers to Grade ≤ 1	Resume at original dose	Apatinib interruption for more than 28 days
	Grade 3	Yes	Until the toxicity recovers to Grade ≤ 1	Reduce the dose by one level	
Hypertension	Grade 3 (after corrective treatment)	Yes	Until the toxicity recovers to Grade ≤ 1	Reduce the dose by one level	Apatinib interruption for more than 28 days
Proteinuria (without significant increase in blood creatinine)	Grade 3 (24-h urine protein quantification)	Yes	Until the toxicity recovers to Grade ≤ 2	Reduce the dose by one level	Apatinib interruption for more than 28 days

Apatinib-Related Toxicities	Grade	Dose Delay or Not	Criteria for Resuming	Dose Modification Method	Criteria for Discontinuation
Hand-and-Foot Syndrome	Grade 3	Yes	Until the toxicity recovers to Grade ≤ 1	Reduce the dose by one level	Apatinib interruption for more than 28 days

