Grade 2 AST/ALT > 3 × ULN, but ≤ 5 × ULN and/or TBIL > 1.5 × ULN but ≤ 3 × ULN	
Delay the immunotherapy according to the study protocol;Increase the monitoring frequency to once every 3 days.	
If symptoms recover to the baseline level:
 
Resume routine monitoring and resume the immunotherapy according to the study protocol. 
If elevation persists for > 5-7 days or aggravates:
 
Intravenous administration of 0.5-1 mg/kg/d methylprednisolone or an equivalent orally administrated dose. If LFT recovers to grade 1 or to the baseline level, reduce the dose of steroids for at least 1 month, and consider prophylactic antibiotics to prevent opportunistic infection and then resume the immunotherapy according to study protocol.
Grade 3-4 AST/ALT > 5 × ULN and/or TBIL > 3 × ULN	
Terminate the immunotherapy according to the study protocol*;Increase the monitoring frequency to once every 1-2 days;Intravenous administration of 1.0-2.0 mg/kg/d methylprednisolone or an equivalent dose via intravenous injection**;Add prophylactic antibiotics to prevent opportunistic infections;Consultation with the gastroenterology department.	
If it recovers to Grade 2:
 
Reduce the dose of steroids for at least 1 month. 
If not improving, or even aggravating or recurring after > 3-5 days:
 
Add mycophenolate mofetil 1 g bid;If the symptoms are not relieved within 3-5 days, other immunosuppressants are considered based on local guidelines.

Once a patient given intravenous injections of steroids shows a sustained clinical improvement, the patient can switch to an equivalent dose of oral corticosteroids (e.g., prednisone) by the time or before the dose of steroid injections starts to be gradually reduced. When switching to oral corticosteroids with an equivalent dose, it should be considered that the bioavailability of oral corticosteroids is relatively low.

* If AST/ALT ≤ 8 × ULN and TBIL ≤ 5 × ULN, the immunotherapy can be delayed rather than discontinued.

**For Grade 4 hepatitis, the recommended starting dose of methylprednisolone intravenous injection is 2 mg/kg/d.

4. Management Principles for Endocrine Adverse Events

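### Subjects with liver metastasis may enter at Grade 2 AST/ALT, but Table 7 allows SHR-1210 to resume only at Grade 0-1 while Appendix 4 names return to baseline; the hepatic rules need reconciling

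*Protocol*

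**What the plan says.** **Entry.** Inclusion 8f, in Protocol 4.1 and the synopsis, sets a limit of 2.5 x ULN for AST *or* ALT. It then adds that "for patients with liver metastasis, ALT and AST should be" at or below 5 x ULN.

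**Grading.** The hepatic table in Appendix 4 defines Grade 2 as "AST/ALT > 3 × ULN, but ≤ 5 × ULN" and Grade 3-4 as above 5 x ULN.

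**SHR-1210, Table 7 (5.2.1).** A related Grade 2 AST/ALT rise interrupts SHR-1210. The resumption cell reads "Recovered to Grade 0-1", with no baseline alternative. The discontinuation cell applies if "Toxicity has not resolved by 12 weeks after the last dose", or if steroids cannot be tapered in that time. Grade 3-4 means discontinuation, and footnote a is attached to that row. It opens "For subjects with liver metastasis and grade 2 AST or ALT increased at baseline" and provides that, if a rise of at least 50% from baseline "persists for at least 1 week, the treatment shall be discontinued".

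**Appendix 4, hepatic rows.** At Grade 2, return to baseline leads to resumption under the protocol. After steroids the condition is "If LFT recovers to grade 1 or to the baseline level". A note to the Grade 3-4 row permits delay instead of discontinuation while AST/ALT is at most 8 x ULN and total bilirubin at most 5 x ULN.

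**Apatinib, Table 9 (5.2.3).** Grade 2 non-hematologic toxicity lasting 7 days or more must fall to Grade 1 or below before dosing resumes. The stopping criterion is "Apatinib interruption for more than 28 days". Baseline is not mentioned.

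**The concern.** Eligibility accepts an enzyme level that the SHR-1210 resumption rule does not. A subject who qualifies at Grade 2, has a drug-related rise and then returns to the entry value has recovered by Appendix 4's measure but not by Table 7's. Followed as written, Table 7 keeps that subject off SHR-1210 at a level the protocol thought acceptable for starting it.

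Footnote a shows that the authors foresaw Grade 2 at baseline, yet it does not say when such a subject may restart. What is at stake is consistent handling of a foreseeable case in an open-label trial where liver metastasis is a planned subgroup (SAP 11.5.3.3).

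The wording of 8f is a second, separate defect. With *or* in the first limit and *and* in the second, a literal reading makes the limit without liver metastasis the looser one.

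**Working it through.** The documents state no figure to reproduce. The check sets the rules side by side and does arithmetic on multiples of ULN.

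**Inputs.** Entry ceiling with liver metastasis: 5 x ULN (8f). Grade 2 band: above 3 and up to 5 x ULN (Appendix 4). Resumption level: Grade 0-1 (Table 7). Footnote a trigger: 1.5 x baseline, lasting at least a week.

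The ceiling of Grade 0-1 is taken as 3 x ULN, the lower bound of the Grade 2 row. The Grade 1 row, in the text available, prints AST/ALT as above 3 x ULN. That overlaps Grade 2 and may be a misprint or a reading error, so it is not used.

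**Formulas.** Fall below entry needed to resume = 1 - 3/entry. Footnote a trigger = 1.5 x entry.

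| Entry (x ULN) | Fall needed to resume under Table 7 | Footnote a trigger (x ULN) | Grade at trigger |
|---|---|---|---|
| 3 or below | none | not applicable | entered at Grade 0-1 |
| 3.33 | 1 - 3/3.33 = 10% | 5.0 | 2 |
| 4 | 1 - 3/4 = 25% | 6.0 | 3 or higher |
| 5 | 1 - 3/5 = 40% | 7.5 | 3 or higher |

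**Case A: entry 4, related rise to 4.8 x ULN, back to 4.** The peak is Grade 2, so Table 7 interrupts. The rise is 4.8/4 - 1 = 20%, below the footnote a trigger. At 4 x ULN the subject meets Appendix 4's recovery level but not Table 7's.

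**Case B: entry 4, related rise to 5.5 x ULN.** The peak is Grade 3 and the rise is 5.5/4 - 1 = 37.5%. Table 7's Grade 3-4 row discontinues. The footnote a trigger of 6.0 is not met. Appendix 4's note permits delay, since 5.5 is below 8, provided bilirubin is within its limit.

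**Case C: entry just above 3 and up to 3.33 x ULN.** The footnote a trigger lies between 4.5 (1.5 x 3) and 5.0 (1.5 x 3.33), inside Grade 2. For the same value, the Grade 2 row says interrupt and the footnote says discontinue.

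**Criterion 8f read literally.** A subject without liver metastasis who has AST 2 x ULN and ALT 8 x ULN satisfies the *or* limit. The same values with liver metastasis fail the *and* limit.

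**Baseline elsewhere in the protocol.** AE follow-up (7.4.1) accepts return to baseline or Grade 1 or below as an end point. Table 12 has a separate column for abnormal baseline liver tests. Follow-up of an event can therefore close while Table 7's resumption level is still unmet.

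**The case against.** The strongest reply is that the protocol already has a route for such cases. Section 5.2.1 requires the investigator to consult the sponsor when a Table 7 adjustment seems inappropriate, and its opening text allows resumption once the toxicity has resolved. The 12-week cell also speaks of resolution rather than a grade, so a subject back at entry level might count as resolved and permanent loss of SHR-1210 does not clearly follow. Appendix 4 describes itself as reference guidance, and its Grade 2 resumption lines defer to the protocol.

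Most of this stands as mitigation. It makes the conflict softer than two binding rules in direct opposition, and central consultation weakens any inference that sites would act differently. But none of these passages states a resumption level for a subject who entered at Grade 2. Appendix 4's deference leads back to the Table 7 cell that such a subject cannot meet at entry level. If the 12-week cell is read generously, the subject may neither resume nor clearly be required to stop.

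Two further objections hold. Table 9 does not conflict with Appendix 4, which covers immuno-oncology drugs and not apatinib; Table 9 merely lacks a provision for the same subjects. The *or* in 8f is probably loose wording, and exclusion 25 lets the investigator keep out subjects with risky laboratory values. A reader might infer that 8f admits subjects whom Table 7 would at once take off treatment. It does not, because Table 7 governs drug-related toxicity on treatment and not entry values.

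**Conclusion.** The inconsistency is real and worth correcting, within narrow limits. It concerns only subjects with liver metastasis who enter above 3 x ULN and then have an SHR-1210-related rise. Those at or below 3 x ULN entered at Grade 0-1, and a stable entry value triggers nothing.

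The number affected cannot be derived, because the documents do not give the share entering at Grade 2. It is probably small. Protocol 1.3.1 reports treatment-related AST increase in 8.2% and ALT increase in 6.7% of 539 subjects given SHR-1210 alone or in combination, and only the part of such events falling on subjects with raised entry values matters here. The rate could be higher with apatinib or with raised baseline enzymes.

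A reader might infer that the mismatch lowers ORR, distorts the liver-metastasis subgroup or tips a go/no-go cut-off. The documents do not support that. Best overall response runs to progression or new anti-tumor treatment (Protocol 7.1.1, SAP 11.5.1.1), and imaging continues after treatment stops (Protocol 6.4). An interruption therefore does not by itself remove a response, and no sample-size or decision figure depends on this point.

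The conclusion rests on reading Grade 0-1 as at most 3 x ULN.

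**What to change.** The sponsor should reconcile three places so that one stated rule covers subjects who enter with Grade 2 AST/ALT: inclusion 8f, in both 4.1 and the synopsis; Table 7 with footnote a; and the hepatic rows of Appendix 4. The reconciliation should settle:

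- what counts as recovery for resuming SHR-1210;
- how footnote a relates to the Grade 2 and Grade 3-4 rows;
- how the Appendix 4 note on delay fits with discontinuation in Table 7;
- whether the *or*/*and* difference in 8f is intended.

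Table 9 should be checked for the same subjects. Which levels and actions apply is for the sponsor's clinicians, and this review takes no position on them.

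The cost is wording in one criterion, one or two tables and one appendix. No tests are added, since AST and ALT are already measured at screening and before each cycle. A few subjects may continue or stop treatment differently, depending on the rule chosen.

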4.2 Exclusion Criteria

Patients meeting any one of the followings are not eligible to participate in this study:

1. Known HER2-positive.
2. Prior treatment with anti-PD-1/PD-L1 antibodies, CTLA-4 antibodies, or other treatments targeting PD-1/PD-L1 and/or VEGFR inhibitors.
3. Known allergies to the study drug or their excipients; severe allergic reactions to other monoclonal antibodies.
4. Having received immunosuppressive drugs within 14 days prior to the first dose of SHR-1210, excluding intranasal and inhaled corticosteroids or systemic steroids of physiological doses (i.e., no more than 10 mg/d of prednisolone or equivalent).
5. Having received live, attenuated vaccines within 4 weeks before the first dose or had such vaccination plan during the study.
6. Presence of known uncontrolled or symptomatic active central nervous system (CNS) metastases, manifested as clinical symptoms, cerebral edema, spinal cord compression, carcinomatous meningitis, leptomeningeal disease, and/or progressive growth. Patients with a history of metastases to the central nervous system or spinal cord compression may be eligible if they are clearly treated and clinically stable 4 weeks after discontinuation of anticonvulsants and steroids before the first dose of study treatment.
7. Presence of Grade > 1 peripheral neuropathy.
8. Advanced diseases that are symptomatic, disseminated to viscera, and at risk of life-threatening complications in the short term (including uncontrollable massive [pleural, pericardial, and abdominal] exudate, pulmonary lymphangitis, and more than 30% of hepatic involvement).
9. Presence of any active autoimmune diseases or a history of autoimmune diseases (including but not limited to autoimmune hepatitis, interstitial pneumonia, uveitis, enteritis, hepatitis, hypophysitis, vasculitis, nephritis, hyperthyroidism, hypothyroidism; adult subjects with vitiligo or completely relieved childhood asthma can be enrolled if they do not require any intervention; patients with asthma requiring medical interventions with bronchodilators cannot be enrolled).
10. Having been diagnosed with any other malignancies within 3 years before the enrollment, excluding adequately treated basal cell carcinoma or squamous cell skin cancer, or cervical carcinoma *in situ*.

11. Infection with human immunodeficiency virus (HIV) or known acquired immunodeficiency syndrome (AIDS), active hepatitis B (HBV DNA \geq 500 IU/mL), hepatitis C (hepatitis C antibody being positive and HCV-RNA being above the lower limit of detection of the assay), or co-infection of hepatitis B and C.
12. Any of the following conditions observed within 6 months prior to the enrollment: myocardial infarction, severe/unstable angina, > NYHA Class II cardiac insufficiency, poorly controlled arrhythmia (including males with QTcF $>$ 450 ms and females with QTcF $>$ 470 ms, QTcF interval calculated with the Fridericia's formula), symptomatic congestive cardiac failure, or cerebrovascular accident (including transient ischemic attack or symptomatic pulmonary embolism).
13. Hypertension uncontrolled by antihypertensives (systolic pressure $>$ 140 mmHg or diastolic pressure $>$ 90 mmHg).
14. Abnormal coagulation function (INR $>$ 1.5 or activated partial thromboplastin time (APTT) $>$ 1.5 \times ULN), bleeding tendency, or receiving thrombolytics or anticoagulant therapy.
15. Known hereditary or acquired hemorrhage and thrombophilia (hemophilia, coagulopathy, thrombocytopenia, hypersplenism, etc.).
16. Obvious hemoptysis or a daily amount of hemoptysis of half a teaspoon (2.5 mL) or more within 2 months before the enrollment.
17. Clinically significant hemorrhage symptoms or clear bleeding tendency within 3 months prior to participation in this study, such as GI bleeding, hemorrhagic gastric ulcer, baseline fecal occult blood++ and above, or vasculitis.
18. Events of arterial/venous thrombosis within 6 months prior to participation in this study, such as cerebrovascular accidents (including transient ischemic attacks, cerebral hemorrhage, and cerebral infarction), deep vein thrombosis, and pulmonary embolism.
19. Known hereditary or acquired hemorrhage and thrombophilia (hemophilia, coagulopathy, thrombocytopenia, hypersplenism, etc.).
20. Requiring long-term anticoagulant therapy with warfarin or heparin; or requiring long-term antiplatelet therapy (aspirin \geq 300 mg/day or clopidogrel \geq 75 mg/day).
21. Complicated with severe infection (such as one requiring intravenous infusion of antibiotics, antifungals, or antivirals) within 4 weeks prior to the first dose, or any unexplained fever of $>$ 38.5 °C observed during screening period/prior to the first dose.

22. Known history of allogeneic organ transplantation or allogeneic hematopoietic stem cell transplantation.
23. Having participated in clinical studies concerning any other drugs within 4 weeks prior to the first dose, or less than 5 half-lives from the last dose of study drugs.
24. Known history of psychotropic substance abuse or drug abuse.
25. Patients with other severe physical or psychiatric disorders or laboratory abnormalities, which may increase the risk of participating in this study or interfere with the study results, as well as those deemed unsuitable by the investigator.

